#### Outcome

The investigators are going to evaluate:

- 1. The implementation, how the clinical organization and the therapists follow the treatment protocol.
  - 2. The waiting time and the frequency of treatment sessions.

- 3. Amount of in-patient care.
- 4. The outcome of the patient, with focus on weight gain and medical stabilization. The investigators will also look at psychological improvement, and evaluate the improvement in specific eating disorders psychopathology and improvement in general psychiatric psychopathology.
  - 5. The health economic cost.

The main outcome variables, such as weight gain, waiting time, frequency of treatment sessions and amount of inpatient care will be compared with the patient and families that have been in treatment before the ROCKETLAUNCH project started.

#### **Data Collection**

# Patient that had been in treatment before ROCKETLAUNCH

Data from the patients who have been in treatment before the project started and meet the medical inclusion criteria will be collected. Data from ten patients at each participating unit on will be collected from the case records.

- The first visit: Age, waiting time from notification to the first time offered and weight and length.
- After one month: Weight. Number of visits to reception and number of visits with family meal. Amount of in-patient care. If the family and patient have been in day care or in-patient care, days of admission will be counted.
- After one year: Weight and length and diagnostic status. Amount of in-patient care. The information about patients before the start of the project will be collected from the same time period at all units.

The data from this early group will be compared with the collected data from the group that will participate in the project.

Weight is regularly monitored in the treatment according to the protocol. These data will include 120 patients from before the project start and approximately 150 patients annually who will enter the project.

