# Research and evaluation

#### Scientific issues

There are four central issues regarding research and evaluation.

- 1. Are the prerequisites for implementing the guidelines for RAKETSTART optimal? The investigators want to make an assessment of how the clinicians who will carry out the treatment in the project will experience opportunities and difficulties.
- 2. Are the waiting times shortened and are the recommended treatment intensity maintained? An important part of the study is to see if the healthcare system can improve its care for these life-threatening conditions.
- 3. Are the patients improved in the expected extent? The amount of patients that gained 2 kg or more before the project has been 23.7% which means that a greater proportion than that of the intervention group should gain 2 kg or more during the first month of treatment. In a study of FBT 35% of the patients gained 1.8 kg during the first 4 weeks (4), which should be the proportion that the investigators aim for.

One particular issue will be to evaluate the effect of family meals that will only be offered to those patients who do not gain weight as expected. The importance of family meals has been very sparingly evaluated in international research (15).

4. Is the financial burden for family and health care reasonable in relation to the effect? Project ROCKETLAUNCH involves an intensive treatment, which places great demands on both healthcare practitioners and the patient and family. In order to safely justify that this effort is reasonable, the investigators are making a health economic evaluation.

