#### Methods

# **Participants**

The inclusion criteria for the patients are that they fulfill one of the three diagnoses Anorexia Nervosa, Atypical Anorexia Nervosa or ARFID and that they are in a pronounced starvation. All patients and their parents that are offered treatment within the ROCKETLAUNCH project and that fulfill the inclusion criteria will be asked to participate in the research. The treatment will take place at Child and Adolescent Psychiatry in the Southern Healthcare Region in Sweden. The Eating Disorder units in Skåne, Halland and Blekinge will participate in the project, AnorexiBulimiCenter in Kalmar and Västervik will also be involved in the project. This means that all patients with severe restrictive eating disorders in Skåne, Halland, Blekinge and Kalmar can be asked to participate in the project. In all it is 12 different out-patient clinics that will give the treatment.

At each out-patient clinic data from the 10 previous patients will be gathered in order to compare the treatment as usual with the ROCKETLAUNCH intervention.

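### Does taking ten control patients per clinic contradict the statement that all units' controls come from the same time period?

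*Protocol*

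**What the plan says.** The Participants section (Protocol, Methods) defines the comparison group by count: "At each out-patient clinic data from the 10 previous patients will be gathered". It gives 12 out-patient clinics.

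The section Patient that had been in treatment before ROCKETLAUNCH repeats the count ("Data from ten patients at each participating unit on will be collected from the case records") and adds eligibility: "Data from the patients who have been in treatment before the project started and meet the medical inclusion criteria will be collected". It gives the total: "These data will include 120 patients from before the project start and approximately 150 patients annually who will enter the project". It then adds the sentence at issue: "The information about patients before the start of the project will be collected from the same time period at all units". No start date, end date or length of period is given for these controls.

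The Introduction describes an earlier mapping by the same working group. It took the ten most recent patients at each unit who came into treatment before 20 November 2016, 60 patients in all.

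**The concern.** A fixed count and a common calendar period are different sampling rules. They coincide only if every clinic sees exactly ten eligible patients in the period. If the ten are the last ten before a date, only that date is shared and the look-back varies by clinic. If a common window is meant, clinics with more than ten need a rule for choosing among them, and clinics with fewer cannot supply ten.

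This group carries the study's comparisons. Under Outcome, weight gain, waiting time, session frequency and in-patient care "will be compared with the patient and families that have been in treatment before the ROCKETLAUNCH project started". The records are read in retrospect with the outcome already in the chart, so a free choice of ten would leave room for selection, and unequal look-backs would leave room for calendar drift.

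A related worry is clinic mix. Each clinic contributes one twelfth of the controls, whereas in the project all patients "that fulfill the inclusion criteria will be asked to participate in the research", so that group follows clinic volume.

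**Working it through.** **The plan's own figure.** 12 clinics × 10 patients = 120, as stated. The count of ten per clinic is therefore the operative rule.

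**How far a fixed count departs from a common period.** Clinic volumes are not given. Assume that the planned 150 patients a year also held before the project, split equally with chance (Poisson) accrual.

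- Volume per clinic: 150 / 12 = 12.5 a year.
- Mean time spanned by ten patients: (10 / 12.5) × 12 = 9.6 months.
- The span at one clinic follows a gamma distribution with shape 10 and scale 12 / 12.5 = 0.96 months. Its 10th to 90th percentile runs from 6.0 to 13.6 months.
- Across 12 such clinics (400,000 simulations), the shortest span averages 5.3 months and the longest 15.1.
- In a common 9.6-month window, the count at each clinic is Poisson with mean 10. P(exactly ten) = 0.125, P(fewer) = 0.458 and P(more) = 0.417. Multiplied by 12, this gives 1.5, 5.5 and 5.0 clinics.

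Unequal volumes widen the spread, but any such volumes would have to be invented. The literal mismatch is present even with identical clinics.

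**Whether the text leaves the choice of ten open.** The statements set side by side:

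| Source in the Protocol | What it fixes |
|---|---|
| Participants | The ten previous patients at each clinic, a definite set |
| Patient that had been in treatment before ROCKETLAUNCH | In treatment before project start; medical inclusion criteria met; 120 in total |
| Same section | A period common to all units, not defined further |
| Introduction (earlier mapping) | Precedent: ten most recent before one shared date |

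The first two rows already select patients: the last ten eligible before the project. The third fits them if it means the period before a shared cut-off, which is how the mapping worked. No section says that ten are drawn from a larger pool. The question of which ten to take arises only if a window is put in place of the Participants rule.

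**Whether a result is shown to move.** An unequal look-back biases the comparison only if usual care changed over those months, and the Protocol reports no such change. The weight-gain benchmark under Scientific issues, "The amount of patients that gained 2 kg or more before the project has been 23.7" per cent, matches the mapping figure in the Introduction, so it does not depend on the disputed sentence.

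**Clinic mix.** The Introduction gives unit mean gains from 0.1 to 1.5 kg, a spread of 1.4 kg. These are six means of ten patients each. The patient-level SD is not given, so assume 1.42 to 2.2 kg: the lower value from (2 − 0.98) / z for 23.7 per cent above 2 kg, the upper from the 10.2 kg range / 4.64.

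- Standard error of a unit mean: 1.42 / √10 = 0.45 kg to 2.2 / √10 = 0.70 kg.
- Expected range of six means with no true unit differences: 2.534 × standard error = 1.14 to 1.76 kg.

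The observed 1.4 kg lies inside that interval, so it is compatible with chance.

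**The case for a change.** The strongest case for a change is that this non-randomised group is the only comparator for the main outcomes, that who enters it is a matter for the protocol and not the SAP, and that a correction would cost only a sentence. The mapping rule is not expressly carried over to the study controls, and even that rule fixes only an end date. A reader who takes the sentence literally is told that calendar time is aligned across clinics when the quota does not ensure it.

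Much of this stands as a comment on wording. The sentence claims more than a fixed count can deliver, and no cut-off date is given. It does not show that the controls are wrongly chosen or that an estimate would shift. The natural clarification, the ten most recent eligible patients before a common date, is what the Participants section and the mapping already convey. The real alternative, all eligible patients in one window, is a trade-off: it aligns calendar time but gives up equal numbers per clinic and the assured 120. With 12.5 patients a year at every clinic, a 12-month window would still leave a given clinic below ten with probability about 0.20.

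The clinic-mix argument bears on the result only if the analysis ignores clinic. The Protocol does not say that it will, and handling of clinic properly belongs to an SAP that is not at hand.

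**Conclusion.** The concern does not call for a change. The sentence about a common time period is loosely worded, and the missing cut-off date is a detail that analysts following the Participants section would fill in the evident way. The total of 120 is correct, equal numbers per clinic is a legitimate choice, and the selection rule can be read from the text.

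Under the equal-volume assumption, look-backs would differ by several months between clinics (about 5 to 15 months from shortest to longest). That measures how imprecise the sentence is; it is not a measure of bias. Any bias depends on drift in usual care, which is unknown and may be nil. The conclusion rests on reading the common period as a common cut-off. If controls were in fact picked freely from a longer window, the selection worry would return, but nothing in the Protocol describes that.

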# Introduction

Restrictive eating disorders with pronounced starvation is one of the most acute and life-threatening conditions in child and adolescent psychiatry. The restrictive eating disorders are Anorexia Nervosa, Atypical Anorexia Nervosa and ARFID.

It is crucial that the treatment of these conditions initially focuses on the starvation and achieves a medical stabilization with weight gain for those with an underweight (1). Recent research has shown that weight gain during the first month of treatment gives a better prognosis (2-5). Family-based treatment has the best support in research to achieve weight gain for adolescents with anorexia nervosa (6). Intensive family treatment initially in treatment, which focuses on putting an end to starvation, has proven to be able to achieve sustainable results even after 30 months (7). However, only 26.4% of children and adolescents with an eating disorder in Sweden receive family therapy according to RIKSÄT, the national quality register for eating disorders (8).

The initial treatment for many young patients with an eating disorder is in-patient care, according to RIKSÄT, it is the first registered treatment for 25% of the patients. This underlines the need for a better treatment effort initially. An early-established evidence-based family therapy in outpatient care can prevent the need for hospitalization at a psychiatric clinic, and also improve the prognosis

In order to improve the treatment that patients with restrictive eating disorder and pronounced starvation within Region Skåne receive today, a working group was started in 2017 with the task of drawing up guidelines for these patients who were treated in Child and Adolescent Psychiatry in Skåne. The working group consisted of representatives from the 5 local child psychiatric units that have eating disorder teams, in Kristianstad, Lund, Ystad, Malmö and Helsingborg, as well as the regional unit at Region Skånes Center of Eating Disorders (RSÄ) in Lund.

In order to get a picture of how the initial treatment for new patients with pronounced restrictive eating disorder that comes into treatment at Child and Adolescent Psychiatry works today, the working group collected information from the units within Child and Adolescent Psychiatry in Skåne. The mapping that was done consisted of the 10 most recent patients who came into treatment before November 20, 2016. The information collected was:

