- From the initial assessment: Age, waiting time from notification to the first time offered and weight and length.
- After one month: Number of visits during the first month and weight after one month. In total, information about 60 patients was collected.

What the working group found was:

- The age is the same, 15.0 years, at start of treatment.
- How quickly you can offer time for the first visit varies between units. For three units it was around three weeks (19.6, 22.3 and 23.7 days respectively). For the other three units around two weeks (12.1, 15.1 and 15.6 days respectively). The working group has agreed that a waiting period of more than two weeks is not acceptable.
- The number of visits during the first month looks quite similar. An average of 6.2 (between 4.7 and 7.6) is just over a visit a week, which seems reasonable since it means on average more than one visit a week. Some of these visits prove to be visits within day care.

- The weight gain for the whole group was on average 0.98 kg, but some patients had lost weight. The range was -4.2 kg -6.0 kg. Of the patients that had a weight below 90%EBW at start of treatment 23.7% gained 2 kg or more during the first month of treatment.
- How much the patients have gained weight during the first month varied between the different units. The average weight gain varied between 0.1 kg and 1.5 kg between the units. It is lower than 2.0 kg, which is the lowest level of weight gain during the first month that international research has proven to be indication of a better prognosis.

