# Implementation Preparation

Before the project starts, the investigators intend to make an employee survey. The purpose of the survey is to provide each clinic with a basis for planning and creating good conditions for the implementation of ROCKETLAUNCH. In the previous research (14), the areas that are affected in the survey have proved to be important for how well one can succeed in implementing new methods and way of working. In previous implementation within Child and Adolescent Psychiatry nationally within the framework of the so-called "Deplyftet", where national guidelines for the treatment of depression were implemented, an employee survey was used to identify impeding and favorable factors. The purpose was that each unit should have knowledge of factors grouped as follows, in order to be able to design its specific implementation plan, factors such as:

- 1. Features of the innovation, the guideline itself and the manuals in this case.
- 2. Features of the user of the guideline, employees.
- 3. Characteristics of the target group, the patients.
- 4. Properties in the social environment and the organization.
- 5. Features in the system, economy and administration
- 6. How close to what is described in the guideline is the way of working today on the unit?

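### The before/after comparison cannot tell background change from a ROCKETLAUNCH effect, and the undated early group and the 2016 benchmark leave the size of that gap open

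*Protocol*

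**What the plan says.** Under Participants, the protocol states: "At each out-patient clinic data from the 10 previous patients will be gathered in order to compare the treatment as usual with the ROCKETLAUNCH intervention". Under Outcome, weight gain, waiting time, session frequency and in-patient care "will be compared with the patient and families that have been in treatment before the ROCKETLAUNCH project started". The Data Collection section repeats this ("The data from this early group will be compared with the collected data from the group that will participate in the project") and gives the sizes: "These data will include 120 patients from before the project start and approximately 150 patients annually who will enter the project". The early patients come from case records, ten per unit, from one period common to all units. No dates are given for that period. No concurrent control or staggered start is described.

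An older data set also exists. The Introduction reports that "The mapping that was done consisted of the 10 most recent patients who came into treatment before November 20, 2016". It covers 60 patients from the Skåne units, with age, waiting time, weight and length, first-month visits and one-month weight. In those below 90% EBW, 23.7% gained at least 2 kg. Question 3 under Scientific issues then uses 23.7% as the rate before the project, without the EBW restriction. The protocol does not say whether the mapped patients are among the 120.

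**The concern.** Every project patient is later than every early patient, so period and treatment coincide. A background improvement would be credited to ROCKETLAUNCH, and a background worsening would hide a real effect.

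The protocol gives reasons not to take constant care for granted. A guideline group of the Skåne units started in 2017, and on waiting times "The working group has agreed that a waiting period of more than two weeks is not acceptable". The employee survey asks each unit: "How close to what is described in the guideline is the way of working today on the unit". Waiting time is one of the main outcomes.

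Questions 2 and 3 ask whether waiting times shorten and patients improve. Those answers will inform whether the project becomes permanent, so it matters how much of a difference can be attributed to it.

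**Working it through.** **Plan figures.** 12 clinics × 10 = 120 early patients, as stated. Six Skåne units (five local, one regional) × 10 = 60 mapped patients, as stated. Project intake is about 150 a year: 300 over two years, 450 over three. With a denominator between 10 and 60, only 9/38 and 14/59 round to 23.7%. The protocol states no alpha or power; two-sided 5% is assumed below.

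**False positives, share gaining 2 kg.** Assume no project effect, p₁ = 0.237, n₁ = 120, n₂ = 300 and a background rise d, so p₂ = p₁ + d. Let s₀ be the pooled and s₁ the unpooled standard error of the difference. Then

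P(reject) = Φ((d − 1.96 s₀)/s₁) + Φ((−d − 1.96 s₀)/s₁).

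For d = 0.05: pooled p = (120 × 0.237 + 300 × 0.287)/420 = 0.2727, s₀ = 0.0481, s₁ = 0.0468, and P = 0.172 + 0.001 = 17.3%.

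| Background rise (points) | 120 v 300 | 120 v 450 |
|---|---|---|
| 0 | 5.0% | 5.0% |
| 3 | 9.3% | 9.6% |
| 5 | 17.3% | 18.4% |
| 7.5 | 32.7% | 35.2% |

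Simulation of the same test at 120 v 300 gave 9.2%, 17.5% and 33.2%.

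**Mean first-month gain.** The SD is inferred from the mapping's range, −4.2 to 6.0 kg: 10.2/4.64 = 2.20 kg, where 4.64 is the expected range, in SD units, of 60 normal values. The simple standard error is 2.20 × √(1/120 + 1/300) = 0.24 kg.

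Assumed layout:
- project start about 2019 (the year in the ethics number);
- mapped patients 3.0 to 2.2 years before start;
- early group in the last 0.8 year before start;
- 300 project patients spread evenly over two years and 12 clinics.

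The midpoints of the early and project periods are then 0.4 + 1.0 = 1.4 years apart. A drift of 0.1, 0.2 or 0.3 kg per year produces a spurious effect of 0.14, 0.28 or 0.42 kg. Simulated false-positive rates are about 9%, 21–23% and 41–43%.

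**Form of the time adjustment.** Two models were simulated with clinic, calendar date and project terms, including the mapped patients. One has a single slope for everyone. The other adds a separate slope within the project, with the effect read at mid-project. With no project effect, both keep the rejection rate near 5% at every drift tested. They differ when there is no drift and a real effect builds linearly to 0.8 kg over year 1 and then holds (two-year average (0.4 + 0.8)/2 = 0.6 kg):

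| Model | Mean estimate | SE | Power |
|---|---|---|---|
| Simple (clinic + project) | 0.60 kg | 0.24 | about 72% |
| Single slope | about 0.31 kg | 0.34 | about 15% |
| Separate project slope | 0.60 kg | 0.39 | about 33% |

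The single slope removes about half of a real effect as trend. The separate slope does not, and its standard error is about 1.65 times the simple one.

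**Responder rate.** Take mapping A (n = 38), early Skåne patients B (n = 60) and project Skåne patients C (n = 150, half of 300). The trend-corrected effect is (C − B) − k(B − A), where k is the gap from B to C divided by the gap from A to B. With 23.7% before and 35% after, k = 1 gives

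SE = √(0.35 × 0.65/150 + 4 × 0.237 × 0.763/60 + 0.237 × 0.763/38) = 0.135.

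For k = 0.5, 1 and 1.5 the SE is 9.7, 13.5 and 17.6 points, against 4.8 for the simple contrast in all 12 clinics. Power for the 11.3-point target (35 − 23.7) falls from 66% to 21%, 13% and 9%.

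**The case against.** The strongest reply is that the protocol states no regression model. It says only that the groups will be compared, and model terms commonly belong in an SAP, which is not at hand. That stands: a reader might infer that a calendar-time term has been wrongly left out, and the document does not support that. The limitation lies in the design, namely which patients and periods are collected.

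Three further inferences also go too far.

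- *That change since 2016–2017 is all credited to the project.* For the group contrast this holds only if the early patients date from then. If they are the last ten before the start, change up to that point is already in the baseline. Early uptake of the guidelines would then raise the baseline and bias towards no effect. Only a comparison with the 23.7% figure necessarily spans everything since 2016.
- *That care was already changing.* The documents show a drafting group, an agreed waiting standard and a survey question. None of these reports a change.
- *That the mapping can separate trend from effect.* It covers six of 12 clinics (counting each Skåne unit as one clinic), is not said to have been screened with the medical inclusion criteria, and has no in-patient data. If its patients turn out to be among the 120, it is not an additional time point.

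A calendar adjustment can itself mislead. Training falls mainly in year 1 and supervision runs for three years, so a growing effect is plausible, and a single shared slope would absorb part of it.

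**Conclusion.** The point holds as a limit on attribution. Background change between the early group and the project period cannot be distinguished from a ROCKETLAUNCH effect, and the 23.7% benchmark adds change since 2016 in a subgroup below 90% EBW. If the true effect is zero, an assumed background rise of 3 to 7.5 points gives about 9% to 33% false positives (120 v 300). An assumed 0.2 to 0.3 kg per year in mean gain gives roughly 21% to 43%.

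These figures rest on a 23.7% starting rate, an inferred SD of 2.2 kg, independent patients, the assumed dates and drift rates that the documents do not supply. They show sensitivity to drift, not that drift occurred. The remedy is a cheap improvement to reporting and sensitivity analysis. It does not turn the design into a controlled comparison.

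**What to change.** 1. Give the calendar dates of the early group, and keep it distinct from the 60 patients mapped in 2016.
2. For waiting time, first-month visits and first-month weight gain, tabulate the six Skåne units by period: 2016 mapping, early group, project year 1, project year 2. Limit mapped patients to those meeting the medical inclusion criteria where the recorded data allow.
3. Beside the simple comparison, report a sensitivity analysis with clinic, calendar date of first visit, project, and a separate slope within the project period, so that an effect building up during year 1 training is not removed as trend.
4. Describe the simple contrast as an uncontrolled before/after association.
5. In question 3, use the early group's own rate as comparator instead of the 2016 figure of 23.7%.

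Cost: some wording, one table and one model; the mapping data already exist. The time-adjusted interval is about 1.65 times wider for mean gain (SE about 0.39 v 0.24 kg) and far less precise for the 2 kg responder rate, and it assumes that the pre-project trend continues linearly. For in-patient care the mapping offers no earlier point, so that outcome stays a plain before/after association.
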